8.2.3 Safety Population

- All subjects who received any study treatment (including control) and reported taking at least one dose but excluding subjects who drop out prior to receipt of the study drug. In the unlikely case a participant receives the incorrect study drug, patients will be grouped according to the treatments that they received in any safety analyses. If a participant receives both placebo and active treatment, they will be considered as receiving active treatment.

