## **4. STUDY INTERVENTIONS**

### **4.1 Treatment of Study Participants**

A summary of the trial’s schedule of events is included in Appendix A.

Timing of study procedures is based on the time of randomization, which is defined as “Time 0”. Study Day 1 is defined as the day of receipt of the first dose of study drug. We will assess the primary outcome on Study Day 15, which corresponds to 14 days (2 weeks) after the initiation of study drug.

A research physician will prescribe a study medication that a central pharmacy (Belmar Pharmacy) will fill at no charge to the patient and will arrive through overnight mail (typically next day by 10:00AM). The study medication will arrive in blinded blister packs labelled as lopinavir/ritonavir or placebo with the appropriate daily instruction for administration. The goal is initiation of treatment within one day of randomization (Study Day 1).

On Study Days 1-15, the patient will complete brief electronic data collection form through a secure electronic platform that will confirm receipt and administration of study drug and document the number and reason for any missed doses. For those with missing electronic data, telephone follow-up will provide an additional opportunity to clarify study drug administration, as needed. If the participant is hospitalized prior to completion of the study medication, an attempt will be made to continue study medication. However, study medication may be discontinued if felt necessary by the treating clinician in consultation with the local investigator. Unblinding will occur only if required for subject safety or treatment at the request of the treating clinician.

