### Telephone/Videophone Data Collection:

While primary data collection will be by electronic methods as above, specific circumstances will trigger telephone or videophone follow-up, based on the following:

- Participant does not complete daily electronic data collection for two consecutive days.
- Participant does not complete Study Day 29 assessment
- Identification of newly prescribed medication if deemed necessary by site investigator.
- New electrocardiogram

- Lack of administration of study medication, if unable to confirm plan to resume study medication
- Hospitalization
- Reported adverse events, if deemed necessary by the site investigator
- Clarification or concern by study team
- By request of participant

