8.2.1 Intention to Treat Population

- All subjects who have receipt of study drug (Study Day 1) based upon their randomized allocation.
- Given the study design whereby patients are shipped study drug from a central pharmacy, there might be times when the drug does not get delivered to the patient. In these rare instances the patient will be excluded. All other subjects will be included, and they will be analyzed according to which group the patient was assigned. Thus, the intent to treat (ITT) analysis set includes all subjects who were randomized and received the study drug at their provided address.

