10.3 Subgroup analyses

The currently recommended approach to subgroup analysis is to prespecify subgroups where there is a clear biological rationale, and otherwise not to create subgroups unless the data indicate differential treatment effects based on potential subgrouping variables. Given how little is known about COVID-19 and possible treatment response, we will examine the potential of differential treatment effects in key subgroups of interest based upon previous definitions unless otherwise noted:

- Age
- Sex
- Race/ethnicity
- BMI
- Baseline renal function defined as known severe chronic kidney disease requiring dialysis, kidney disease not requiring dialysis, no known history of kidney disease
- Hypertension
- Diabetes defined as diabetes with complications, diabetes without complications, not diabetic

- Cardiovascular disease
- Duration of respiratory symptoms prior to randomization

Interactions will not be tested together within the same model but will be tested one by one. Potentially significant subgroups will be identified by evaluating the posterior weight assigned to a model with and without the interaction by Bayesian stacking. If the model including the interaction has a posterior weight of 80% or greater, we will proceed with fitting the model within subgroups. For continuous variables, graphical methods will be used to show how the treatment effect changes over the range of the continuous variable.

11 Safety Analyses

The safety analysis set will be used for safety analyses. Summary statistics will be calculated as described in Section 9. When calculating the incidence of adverse events, or any sub-classification thereof by treatment, time period, severity, etc., each subject will only be counted once for a given safety outcome and any repetitions will be reported separately; the denominator will be the total safety population size.

Three tables summarizing adverse events will be created:

- All-Cause Mortality: A table of all anticipated and unanticipated deaths due to any cause, with number and frequency of such events in each arm/group of the clinical study.
- Serious Adverse Events: A table of all anticipated and unanticipated serious adverse events, grouped by organ system, with number and frequency of such events in each arm/group of the clinical study.

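### The safety set requires a reported dose, so a participant with confirmed delivery who dies or is permanently lost before any dose report is missing from the SAP Section 11 safety tables, including the table of all deaths

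*SAP*

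**What the plan says.** SAP 8.2.3 sets two conditions for the safety set, receipt and a report of dosing: "All subjects who received any study treatment (including control) and reported taking at least one dose". It does not say who must make the report or by when, and no rule covers a participant whose drug arrived but whose dosing is unknown.

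SAP Section 11 states: "The safety analysis set will be used for safety analyses". For adverse event incidence, "the denominator will be the total safety population size". Three tables follow: all-cause mortality, serious adverse events and other adverse events. The first is described as "A table of all anticipated and unanticipated deaths due to any cause".

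The efficacy set is wider. SAP 8.2.1 says that the intention-to-treat "analysis set includes all subjects who were randomized and received the study drug at their provided address", with no dose report required.

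Dosing is recorded on the participant's daily electronic form, which is to "confirm receipt and administration of study drug and document the number and reason for any missed doses" (Protocol 4.1). If the form is missing, "telephone follow-up will provide an additional opportunity to clarify study drug administration, as needed". Protocol Section 6 lists the triggers for a call. One is "Participant does not complete daily electronic data collection for two consecutive days" and another is hospitalization.

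**The concern.** A safety table should hold every known serious event in people who may have been exposed. Here entry depends on a report from the participant, while the events themselves can be learned in other ways. Daily status draws on the Day 29 chart review as well as the surveys (SAP 5.3 and 9.3), and hospital data may come from an alternate contact (Protocol 5.1). Serious adverse events are collected after randomization through Study Day 16, with no dose-report condition (Protocol 11.3). The plan can thus collect a death or serious event and then remove the participant from numerator and denominator alike.

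Exclusion of this kind is unlikely to be random. Those who never report can include people who deteriorate very early and people who give up because of intolerance. Protocol 9.1.2 names gastrointestinal events among the most frequent reactions to the drug and links diarrhea to poorer compliance, so loss that differs by arm is plausible. At stake are a mortality table whose title claims more than its content and serious event tables that may be incomplete.

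**Working it through.** **Who is excluded.** The two definitions, applied to the possible cases after delivery:

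| Participant, drug delivered | ITT set (8.2.1) | Safety set (8.2.3) |
|---|---|---|
| Hospitalized early, dose reported later by telephone | in | in |
| Silent for two days, dose reported when called | in | in |
| Dies before any dose report | in | out |
| Permanently lost before any dose report, event found by chart review | in | out |
| Reported to have taken no dose | in | out |

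The third and fourth rows are the problem. The last row is a proper exclusion from an exposure-based set.

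**Inputs.** The documents give no size for the safety set and no rate of missing dose reports, so there is no plan figure to reproduce for either. SAP Section 7 gives 600 enrolled (540 / 0.90 = 600), hence 300 per arm at 1:1, and example death proportions of 1% and 0.6%. The 0.6% is consistent with the design odds ratio: (0.01/0.99)/1.75 = 0.00577, a probability of 0.57%, which rounds to 0.6%.

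**Expected deaths.** Placebo 300 × 1% = 3.0. Active 300 × 0.6% = 1.8. Total 4.8.

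**Effect of one exclusion.**
- Share of the arm's expected deaths: 1/3.0 = 33% (placebo) and 1/1.8 = 56% (active).
- One placebo death dropped: 3/300 = 1.00% becomes 2/299 = 0.67%. Two dropped gives 1/298 = 0.34%.
- With active at 1.8/300 = 0.60%, one lost placebo death shrinks the difference from 0.40 to 0.07 percentage points.
- One lost active death gives 0.8/299 = 0.27% and widens the difference to 0.73 points.

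The direction therefore depends on which arm loses the death.

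**Range under assumptions.** Let m be the share of participants, and e the share of deaths, with no dose report. Both are assumed. Tabulated mortality is deaths × (1 − e) / [300 × (1 − m)].

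| e | m | Placebo (true 1.00%) | Active (true 0.60%) |
|---|---|---|---|
| 0 | 5% | 1.05% | 0.63% |
| 10% | 10% | 1.00% | 0.60% |
| 25% | 5% | 0.79% | 0.47% |
| 50% | 2% | 0.51% | 0.31% |

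The first row shows that the rule can also raise a rate, when those removed had no event.

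**How many deaths might be lost.** If m is 2% to 5% (assumed), 6 to 15 per arm leave the set. At the example mortality they carry 6 × 1% = 0.06 to 15 × 1% = 0.15 placebo deaths, and 6 × 0.6% = 0.04 to 15 × 0.6% = 0.09 active deaths. At five times that mortality, the figures are 0.30 to 0.75 and 0.18 to 0.45. Under these assumptions the expected loss is below one death per arm.

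**The case against.** Requiring evidence of at least one dose is a recognised, exposure-based way to define a safety set. SAP 8.2.3 sets no deadline, so any later report admits the participant. Both hospitalization and two missed days prompt a call, SAP 4.1 says that missed surveys lead to telephone completion, and Protocol Section 6 expects the questions to be answerable in hospital.

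A reader might infer that anyone hospitalized or unresponsive early drops out of the safety tables. The documents do not support that. Only death or permanent loss of contact before any report has this effect.

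A reader might also infer that the rule biases the comparison toward reassurance. That is not shown either. Numerator and denominator go together, and losing early deteriorators from placebo would count against the drug.

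The deaths are also not invisible. Death and hospitalization are levels of the primary scale, analysed in the ITT set (SAP 10.1). Mortality and hospitalization to Day 29 are secondary endpoints without a dose condition (SAP 5.3), disposition reports dropouts by arm with reasons including death (SAP 9.2), and every death is reported to the DSMB (Protocol Appendix C).

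All of this stands and limits the point. It does not remove it. None of these routes corrects the Section 11 tables, and none returns non-fatal serious events to them. SAP 10.2 also names no analysis set for the secondary endpoints.

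**Conclusion.** The point holds in this limited form. It is a stated rule that produces an incomplete table, not merely a missing detail: the SAP 8.2.3 set does not match the Section 11 claim to tabulate all deaths. It affects participants with confirmed delivery who die or are permanently lost before any dose report and are not recovered by telephone.

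Their number is probably small and cannot be derived from the documents. The non-report shares used above are assumptions, and the death rates come from what the SAP offers as an example. The loss of a whole death is a possibility, not the expected result, but with about 3.0 and 1.8 deaths expected per arm, a single one would be 33% or 56% of an arm's expected deaths. The direction of any between-arm bias is unknown. The primary efficacy analysis is not affected. The change should be made, and before unblinding, since SAP 8.2 fixes set membership by then.

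**What to change.** In SAP 8.2.3, include all randomized participants with confirmed delivery unless it is positively confirmed that no dose was taken. Apply this at least to the all-cause mortality and serious adverse event tables. Report the number with unknown dosing by arm, and show self-reported adverse event rates also among those with a reported dose.

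The change is about one sentence in 8.2.3 plus these reporting lines in Section 11. It needs no new data collection, because delivery already decides ITT membership.

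There are two costs. A few undosed or silent participants enter the denominator. If 5% of the enlarged set were silent and had no self-reported events, those rates would fall to 0.95 of their value, which is why the second display is needed. The safety-set replication of the primary analysis (SAP 10.1.1) would also lie closer to the ITT analysis and add less to it.

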### **4.4 Co-Interventions**

This trial will control the use of lopinavir/ritonavir, or placebo during the 14-day intervention period. Enrolled participants will not receive open-label lopinavir/ritonavir during the 14-day intervention period, unless the patient is hospitalized, and the treating clinician wishes to unblind the trial and use these medications open label. The treating clinicians will make all other treatment decisions without influence from the protocol. Administration of other antiviral, immunomodulatory, or other COVID-19 directed novel medications (“rescue therapy”) will be allowed. We will record the co-administered COVID-19 directed medications in the case report form. The patient will be allowed to take antipyretics at home as needed.

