For patients who experience clinical deterioration requiring hospitalization or toxicity potentially related to study drug, for which treating clinicians feel optimal care would include stopping the study drug and unblinding group assignment, we will stop the study drug, and the site investigator will contact the coordinating center to receive the unblinded study group assignment. We will defer any additional treatments to the treating clinicians. In this situation, we will record the following data in the case report form: the criteria met for clinical deterioration; the reason for stopping study drug and unblinding; use of other antivirals, and immunomodulators; and study outcomes. Crossovers from placebo to lopinavir/ritonavir will be recorded and reported to the DSMB at DSMB reviews and interim analyses. The primary analysis will be intention-to-treat.

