## 6.1 Baseline Variable Collection

- Informed Consent Document and documentation of consent process
- Presence or absence of each inclusion and exclusion criterion
- Date and time of enrollment
- Day of symptom onset
- Specimen type, date, and result of SARS-CoV-2 testing conducted clinically.
- Demographics (age, sex, race, ethnicity, height, weight)
- Comorbidities: chronic cardiac disease, chronic pulmonary disease, chronic kidney disease, chronic liver disease, chronic neurological disease, malignant neoplasm, chronic hematologic disease, AIDS/HIV, obesity, diabetes with complications, diabetes without complications, rheumatologic disorder, malnutrition, smoking, other
- Chronic use of medication: ACE inhibitors, angiotensin receptor blockers
- Receipt of azithromycin in the past week
- Presenting signs and symptoms, along with self-reported severity

## 6.2 Daily Assessments between Randomization and Study Day 16, and then at Day 29

- Study drug administration and reason for missed doses.
- Modified COVID Ordinal Outcomes Scale
- Daily signs and symptoms, along with self-reported severity via electronic log and/or telephone interview.
- Day of symptom resolution
- Receipt of open label antivirals: chloroquine, hydroxychloroquine, remdesivir, lopinavir/ritonavir, other
- Receipt of open label immunomodulators between enrollment and hospital discharge: corticosteroids, tocilizumab, sarilumab, interferon  $\beta$ , other
- Receipt of azithromycin
- Study days in hospital (if applicable)
- Study days receiving supplemental oxygen (if applicable)
- Study days receiving non-invasive or invasive mechanical ventilation (if applicable)
- Study days in ICU to Study Day 29
- Study day of death (if applicable)
- Safety Outcomes: seizure, atrial or ventricular arrhythmia, cardiomyopathy, cardiac arrest, aspartate aminotransferase or alanine aminotransferase levels that are greater than twice the local upper limit of normal (or two times higher than known baseline), acute pancreatitis (defined by a clinically obtained lipase level above the local upper limit of normal and abdominal pain or vomiting), stage II or greater acute kidney injury according to KDIGO criteria, receipt of new renal replacement

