### **9.1.3 Potential risks of receiving placebo with COVID-19**

One potential risk to participating in this study is receiving placebo rather than lopinavir/ritonavir. This risk is only relevant if lopinavir/ritonavir are ultimately found to be an effective therapy for COVID-19 and is not relevant if lopinavir/ritonavir are both ultimately found to be ineffective therapy for COVID-19. This trial protocol minimizes this risk through rigorous design to minimize the number of patients that we must enroll to determine whether these therapies are an effective therapy for COVID-19 and allocating approximately one-third of eligible patients to placebo (instead of one half in a traditional two-arm trial). We will also exclude patients who decline to participate because they feel their optimal care requires lopinavir/ritonavir, exclude patients whose treating clinicians declines to allow enrollment because they feel the patient's optimal care requires treatment with lopinavir/ritonavir, and specify procedures for stopping the study drug, unblinding, and allowing open-label administration of lopinavir/ritonavir for patients who experience clinical deterioration during the study period.

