5.2 Treatment arms

The active treatment arm of lopinavir/ritonavir (LPV/r) consists of standard dosing with 400mg/100mg taken orally twice daily for 28 doses. Medication dose packs contain all 28 doses labelled by study day. The LPV/r dosing is based upon extensive PK/PD study evaluations in healthy and HIV+ subjects.

The control arm consists of unmatched placebo taken orally twice daily for a total of 28 doses. Medication dose packs will contain all 28 doses labelled by study day. Given the unmatched placebo pill to LPV/r, exclusion will be exercised to ensure two individuals from the same household are not enrolled in the study and that telephone assessments during the study avoid discussion of the appearance of the study medication.

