10.1.1 Secondary Analyses of Primary Efficacy Endpoint

We will replicate the primary analyses using the per protocol dataset and the safety dataset.

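### As worded, the SAP 8.2.3 rule on receiving both treatments would count placebo participants who get open-label lopinavir/ritonavir after hospitalization as active, biasing the safety-set results against the drug

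*SAP*

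**What the plan says.** SAP 8.2.3 defines the safety population as those who received study treatment and reported at least one dose. It then deals with dispensing errors: "In the unlikely case a participant receives the incorrect study drug, patients will be grouped according to the treatments that they received". The next sentence is the rule at issue: "If a participant receives both placebo and active treatment, they will be considered as receiving active treatment". It sets no limit by source of the drug, timing or reason. SAP 5.2 identifies the active treatment: "The active treatment arm of lopinavir/ritonavir (LPV/r) consists of standard dosing".

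The protocol foresees placebo participants receiving that drug outside the study supply. Protocol 4.4 bars open-label use during the 14-day intervention period "unless the patient is hospitalized, and the treating clinician wishes to unblind the trial and use these medications open label". Protocol 9.1.3 lists, among its procedures, "allowing open-label administration of lopinavir/ritonavir for patients who experience clinical deterioration during the study period". Protocol 4.6 adds: "Crossovers from placebo to lopinavir/ritonavir will be recorded and reported to the DSMB at DSMB reviews and interim analyses". The daily assessments in Protocol 6.2 capture the exposure: "Receipt of open label antivirals: chloroquine, hydroxychloroquine, remdesivir, lopinavir/ritonavir, other".

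The safety population feeds two outputs. SAP Section 11 uses it for the all-cause mortality, serious adverse event and other adverse event tables, counting each subject once per outcome. SAP 10.1.1 adds: "We will replicate the primary analyses using the per protocol dataset and the safety dataset".

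**The concern.** Within the intervention period, a placebo participant can reach open-label lopinavir/ritonavir only through hospitalization. If receiving it changes the analysis group, group membership becomes a consequence of the outcome. The admission arose on placebo, yet it would be charged to the drug, along with every symptom day and event before it. No text in SAP 8.2.3 or Section 11 splits a participant's events at the first active dose.

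The movement is one-way. A participant assigned lopinavir/ritonavir who gets it open label stays active, while a placebo participant who gets it leaves placebo. The placebo group loses some of its worst outcomes and the active group gains them. At stake are a possible false harm signal in the mortality table and a safety-set rerun of the primary model that understates any benefit.

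**Working it through.** **1. Does the rule reach open-label use?** The case it would catch is placebo study drug, then hospitalization, unblinding and open-label lopinavir/ritonavir. That participant has received placebo and has received the drug that SAP 5.2 calls active. Read literally, the rule applies. The neighbouring sentence on incorrect study drug suggests a narrower intent, but nothing in the section imposes it. SAP 8.2.2 ties per-protocol classification to confirmation by the study pharmacy; SAP 8.2.3 has no such anchor.

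**2. Design figures.** The illustration uses the SAP Section 7 example table, so that table is checked first. Whitehead's formula for 1:1 allocation is N = 12(z₁ + z₂)² / [ln(OR)² (1 − Σp̄³)]. With z₁ = 1.960, z₂ = 1.282, OR = 1.75 and Σp̄³ = 0.2435 from the two columns averaged, N = 12 × 10.51 / (0.3132 × 0.7565) ≈ 532, against 540 stated (within 3%). Then 540 / 0.90 = 600, or 300 per arm.

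**3. Inputs.**
- Levels 1–4 (dead or hospitalized), placebo: 1 + 3 + 4 + 3 = 11%, which is 33 of 300.
- Levels 1–4, active: 0.6 + 1.8 + 2.4 + 1.9 = 6.7%, about 20 of 300.
- Crossovers k: not given in the documents. Assumed 3, 7 or 10, which is 9%, 21% or 30% of the 33.
- Day 15 levels 1–4 stand in for hospitalization or death.

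**4. Proportional odds model, the type used in the SAP 10.1.1 rerun.** A single-day, unadjusted model was fitted to the seven example proportions (300 per arm), moving k placebo participants, spread pro rata over levels 1–4, into the active arm. OR above 1 favours the drug.

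| k | Design benefit | No true effect |
|---|---|---|
| 0 | 1.74 | 1.00 |
| 3 | 1.61 | 0.94 |
| 7 | 1.46 | 0.86 |
| 10 | 1.36 | 0.80 |

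**5. Hospitalization-or-death dichotomy.** Here OR above 1 is against the drug. With a events in the active arm before the move, OR = (a + k) × 267 / [(300 − a)(33 − k)].
- No true effect (a = 33) reduces to (33 + k)/(33 − k): 36/30 = 1.20 (95% CI 0.72–2.01), 40/26 = 1.54 (0.91–2.59), 43/23 = 1.87 (1.10–3.19).
- Design benefit (a = 20): 20 × 267 / (280 × 33) = 0.58 with none moved; 23 × 267 / (280 × 30) = 0.73 with 3; 27 × 267 / (280 × 26) = 0.99 with 7.
- One or two crossovers and no true effect: 34/32 = 1.06 and 35/31 = 1.13.

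**6. Deaths.** The example implies 1% × 300 = 3 placebo deaths. With no true effect, moving 20% of them changes the expected split from 3.0 vs 3.0 to 2.4 placebo vs 3.6 active; moving 50% gives 1.5 vs 4.5.

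**The case against.** The best defence is that the rule is about study-supplied product. It follows directly on the incorrect-drug sentence, SAP 9.4 treats shipping errors as major deviations, and the protocol has its own vocabulary (open label, co-intervention) for hospital use. That is probably what was meant, and it makes the repair easy. It does not remove the problem, because the sentence carries no such limit and two competent programmers could produce different mortality tables.

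Counting anyone exposed to the drug as active is also a recognised cautious choice for safety summaries. That is reasonable for events after exposure. It gives no reason to attribute earlier events to a drug not yet taken.

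Several limits on scope stand:
- A reader might infer that the trial's main conclusion is at risk. It is not. SAP 8.2.1 analyses the ITT set by assigned group, SAP 10.1 runs the primary model on that set, and SAP 8.5.4 bases stopping on the primary-outcome OR.
- A reader might infer that a real benefit would vanish at about 7 crossovers. That holds only for the dichotomy. In the type of model SAP 10.1.1 reruns, 7 crossovers leave an OR near 1.46.
- A reader might infer that the adverse event tables would fill with moved hospitalizations. Protocol 11.2 and Appendix C.3 exempt study outcomes from adverse event reporting unless judged related or of uncertain relationship, so most would not appear there.
- Nothing supports a large crossover count. Protocol 2.1.2 reports that the trial in hospitalized patients failed to show benefit, which gives no reason to expect heavy in-hospital use.

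The DSMB receives crossovers (Protocol 4.6) and every death by coded group (Appendix C). That helps monitoring but does not correct the final tables.

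**Conclusion.** The point holds as a wording fault with a fixed direction of bias and an unknown size. Followed literally, SAP 8.2.3 moves placebo participants who cross over, with their pre-crossover admissions and any later deaths, into the lopinavir/ritonavir group. This affects the all-cause mortality table, whichever adverse events are reportable, and the safety-set rerun of the primary model. With one or two crossovers the shift is small. With the assumed 3 to 10 it is visible in the ordinal OR and larger in the dichotomy.

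The figures rest on the SAP Section 7 example rates, 300 per arm, crossovers drawn pro rata from levels 1–4, and a single-day unadjusted model. The planned rerun is longitudinal, covariate-adjusted and Bayesian, so they are indicative only. The documents support a should-fix correction, not a claim that the trial's primary result is compromised.

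**What to change.** - **SAP 8.2.3:** limit the rule on receiving both treatments to study-supplied product, that is, dispensing errors. Group all other participants by the study product first taken.
- **SAP Section 11:** for placebo participants who later receive open-label lopinavir/ritonavir, count events before the first open-label dose under placebo and list later events, deaths included, on a separate post-crossover line.
- **SAP 10.1.1:** run the safety-set replication of the primary model on the same grouping.

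This changes SAP text only and leaves clinical management alone. The protocol already records open-label use and crossovers (4.4, 4.6, 6.2); programming should confirm that the date of the first open-label dose can be derived. The cost is one extra line in the safety tables. The change should be made before the blind is broken for the final analysis, the point by which SAP 8.2 requires population membership to be set.
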